Appendix 7. Abbreviations

Abbreviation	Definition
ADT	Androgen deprivation therapy
AE	Adverse Event
ALT	Alanine aminotransferase
AST	Aspartate aminotransferase
AUC	Area under the curve
AUC _{0-∞}	Area under the curve from time zero to infinity
BCG	Bacillus Calmette-Guerin
BICR	Blinded independent central reviewer
BPI-SF	Brief Pain Inventory (Short Form)
BUN	Blood urea nitrogen
Ca	Calcium
CFR	Code of Federal Regulations
CI	Confidence interval
CIOMS	Council for International Organizations of Medical Sciences
CIF	Clinical information form
CK	Creatine kinase
Cl	Chlorine
C _{max}	Maximum plasma concentration
CO ₂	Carbon dioxide
COVID-19	Coronavirus disease 2019
CRF	Case report form
CRPC	Castration-resistant prostate cancer
CSR	Clinical Study Report
CT	Computed tomography
CTCAE	Common Terminology Criteria for Adverse Events
CTIS	Clinical Trials Information System
CT SAE	Clinical trial serious adverse event
C _{trough}	Predose trough plasma concentration
CYP	Cytochrome P450
DIL	Dear Investigator Letter
DILI	Drug-induced liver injury
EC	Ethics committee (global term including institutional review boards, independent ethics committees, research ethics committees, and the like)
ECG	Electrocardiogram
ECOG	Eastern Cooperative Oncology Group
eCRF	Electronic case report form
EDC	Electronic data capture
E-DMC	External data monitoring committee
EDP	Exposure during pregnancy
EMBARK	Safety and Efficacy Study of Enzalutamide Plus Leuprolide in Patients With Nonmetastatic Prostate Cancer
EORTC	European Organization for Research and Treatment of Cancer
ePRO	Electronic patient-reported outcome
EQ-5D-5L	European Quality of Life 5-Dimensions 5-Levels Health Questionnaire
EU	European Union
FACT-P	Functional Assessment of Cancer Therapy-Prostate
FDA	Food and Drug Administration
FU	Follow-up
GCP	Good Clinical Practice

Abbreviation	Definition
GGT	Gamma-glutamyl transferase
HR	Hazard ratio
IA	Interim analysis
IB	Investigator's Brochure
ICD	Informed consent document
ICH	International Council for Harmonisation
ID	Identification
INR	International normalized ratio
IP	Investigational Product
IPCW	Inverse probability of censoring weighting
IRB	Institutional Review Board
ITT	Intent-to-treat
IWRS	Interactive web response system
K	Potassium
LFT	Liver function test
LHRH	Luteinizing hormone-releasing hormone
LT	Long term
LTFU	Long-term follow-up
MedDRA	Medical Dictionary for Regulatory Activities
MFS	Metastasis-free survival
Mo	Months
MRI	Magnetic resonance imaging
na	not applicable
Na	Sodium
OL	Open-label
OS	Overall Survival
PACL	Protocol Administrative Change Letter
PCD	Protocol completion date
PCR	Polymerase chain reaction
PET	Positron-emission tomography
PFS2	Progression-free survival on first subsequent therapy
PK	Pharmacokinetic
PROSPER	Prospective Study of Pravastatin in the Elderly at Risk
PSA	Prostate-specific antigen
PSADT	Prostate-specific antigen doubling time
PT	Prothrombin time
q	Every
QLQ-PR25	Quality of Life Questionnaire-Prostate 25 module
RPSFTM	Rank-preserving structural failure time model
RECIST 1.1	Response Evaluation Criteria in Solid Tumors, version 1.1
SAE	Serious Adverse Event
SAP	Statistical Analysis Plan
SARS-CoV-2	Severe acute respiratory syndrome coronavirus 2
SOA	Schedule of activities
SOC	Standard of care
SOP	Standard operating procedure
SPARTAN	A Study of Apalutamide (ARN-509) in Men With Non-Metastatic Castration-Resistant Prostate Cancer
SRSD	Single reference safety document
STAMPEDE	Systemic Therapy in Advancing or Metastatic Prostate Cancer: Evaluation of Drug Efficacy
SUSAR	Suspected unexpected serious adverse reaction

Abbreviation	Definition
TBili	Total bilirubin
ULN	Upper limit of normal
US	United States
Wk	Week

18. SUPPLEMENT 1: OPEN-LABEL STUDY PERIOD

NOTE: This supplement contains cross-references to the main protocol text where study procedures are to be performed in the same manner.

18.1. Rationale and Treatment Plan

Primary endpoint analyses demonstrated that the primary efficacy endpoint of metastasis free survival (MFS) was established and the safety profile of enzalutamide was confirmed, therefore, the treatment codes for all patients will be unblinded and an open-label treatment period is being implemented. The final analysis of the key secondary endpoint for overall survival (OS) will be performed as planned. Patients will continue to receive their originally assigned study treatment in this open-label (OL) study period. Patients assigned to the placebo plus leuprolide arm will no longer take the placebo capsules. No crossover treatment will be implemented.

For patients whose cancer has not progressed radiographically, locally (change was effective as of 31-Mar-2023) performed scans (CT/MRI and bone scan) will be conducted until the patient's cancer progresses radiographically. Scans read centrally by blinded independent central reviewer (BICR) ceased as of 31-Mar-2023. Prostate-specific antigen (PSA) levels will also be done at a local lab and monitored by the investigator per standard of care (SOC) effective date of 31-May-2023. Patients who are in treatment suspension (due to prior undetectable PSA at study Week 36) will continue to have their PSA values, done at the local lab, evaluated by the investigator every 3 months for possible treatment reinitiation per protocol criteria. For details, refer to [Table 16](#).

Patients who discontinue study treatment or withdraw consent for further treatment will continue safety follow-up and long-term follow-up assessments per protocol (see [Section 18.8](#)). Long-term follow-up data including survival status, documentation of new antineoplastic therapies for prostate cancer, skeletal-related events, and progression on first subsequent therapy (PFS2) will be collected every 12 weeks until the final OS analysis. The associated endpoints will be summarized descriptively at the time of the final OS analysis.

Patients who receive any treatment other than their assigned study treatment for prostate cancer after unblinding will not be eligible for this OL period. All patients who permanently discontinue study drug treatment will remain in the study, complete safety follow-up, and subsequently commence long-term follow-up.

Randomized study drug treatment must be permanently discontinued upon initiation of systemic anti-prostate cancer therapy (eg, bicalutamide, nilutamide, or flutamide).

The Brief Pain Inventory (Short Form) (BPI-SF) and quality of life measurements including the Functional Assessment of Cancer Therapy-Prostate (FACT-P) questionnaire, European Quality of Life 5-Dimensions 5-Levels Health Questionnaire (EQ-5D-5L), and the Quality of Life Questionnaire-Prostate 25 (QLQ-PR25) module are no longer required as of 31-Mar-2023.

Table 16. Supplement Table 1: Study Schedule of Activities (Open-Label Period)

Study Period or Visit Abbreviations used in this table may be found in Appendix 7	Treatment			Un- scheduled	Safety FU	Long- Term FU
	1	Wk 13 & Every 12 wks	Wk 25 & Every 6 months			
Study Week	1	85	169	Varies [2]	Varies [3]	Every 12 wks
Study Day	1 [1]	85	169	na	na	Every 84 days
Windows [4]	na	±5	±7	na	±7	±7
General Activities						
Informed consent [5]	X					
Brief physical examination [6]	X	X	X	X	X	
Radiographic assessments CT/MRI, Bone Scan (local) [7]			X	X		X [8]
Symptomatic skeletal events [9]		X	X	X	X	X
Serious and non-serious AE monitoring [10]		X		X	X	
Concomitant medications review [11] and contraceptive check [12].	X	X	X	X	X	X
Enzalutamide dispensing (via IWRS) [13]	X	X		X [14]		
Leuprolide injection [15]	X	X		X [14]		
Study drug accountability		X			X	
Local laboratory evaluation [16]	X	X	X	X	X	
Prostate Specific Antigen (PSA) [18]	X	X		X [17]		
Safety and Long-Term Follow-up Assessments [19]	X				X	X

- OL Day 1 will be the next regularly scheduled visit following approval and activation of this protocol amendment at the study site.
- Anytime necessary to assess or follow-up adverse events, at the patient's request, or per investigator decision.
- Approximately 30 days after the last dose of study drug. If a new antineoplastic treatment is initiated before 30 days after the last dose of study drug, then safety follow-up will occur immediately before starting the new treatment.
- Drug supply must be taken into account if a window is used to schedule the next visit. Visits may be split across the window to allow for drug resupply and completion of study procedures.
- Must obtain informed consent before performing any study specific procedures. This is applicable for all patients participating in the Open-Label Period regardless of those on treatment.
- Symptom directed and includes investigating any new abnormalities and assessment of vital signs per Institution's SOC.
- Per Institution's SOC, refer to Section 18.3.3 for radiographic assessments (CT Scan/MRI/Bone scan).
- For patients who permanently discontinue randomized study drug treatment before radiographic progression is identified and confirmed by local radiology review per protocol, continue radiographic assessments every 24 weeks (± 14 days) until radiographic progression is identified and confirmed by local radiology review per protocol. Refer to Section 18.3.3.
- Record use of radiation therapy (external beam radiation therapy or radionuclides) or surgery to bone for prostate cancer, findings of clinically apparent pathologic bone fracture or of spinal cord compression, and use of opiate and/or systemic antineoplastic therapy due to bone pain. Refer to Section 9.1.3.6.
- Collect serious and nonserious adverse event information from the time of signing of informed consent through safety follow-up. If no safety follow-up, collect adverse event information through 30 days after the last dose of study drug. Contact patients for survival follow-up if they do not come to the clinic per Section 8.
- Only new concomitant medications for prostate cancer, hormonal, antineoplastic therapies and opiates

Table 16. Supplement Table 1: Study Schedule of Activities (Open-Label Period)

Study Period or Visit Abbreviations used in this table may be found in Appendix 7	Treatment			Un-scheduled	Safety FU	Long-Term FU
	1	Wk 13 & Every 12 wks	Wk 25 & Every 6 months			
Study Week	1	Wk 13 & Every 12 wks	Wk 25 & Every 6 months	Varies [2]	Varies [3]	Every 12 wks
Study Day	1 [1]	85	169	na	na	Every 84 days
Windows [4]	na	±5	±7	na	±7	±7

should be reported per Section [18.6](#).

12. Contraceptive review per Section [8.2.3](#) applicable through 3 months after the last dose of study drug or per local guidelines.
13. Specific study drug treatment (ie, enzalutamide, enzalutamide plus leuprolide, or leuprolide) is based on randomized treatment assignment.
14. For patients resuming study drug after treatment suspension, if applicable.
15. Leuprolide acetate (leuprorelin acetate), 22.5 mg will be given as a single intramuscular or subcutaneous injection once every 12 weeks.
16. Performed, collected and assessed locally per Institution’s SOC. Hematology and serum chemistry. Report any clinically significant abnormalities as adverse events per CTCAE v4 criteria. PSA levels for patients in treatment suspension should be entered into the study database.
17. If missed during regularly scheduled visit.
18. Perform and assess PSA locally. Evaluate if PSA value meets threshold for treatment reinitiation in patients on treatment suspension, if so study drug dispensing should be arranged. The investigator to monitor PSA values for PSA progression. Refer to Section [18.3.4](#).
19. May obtain at clinic visits, by telephone contact, chart review, etc. Includes survival status, new antineoplastic therapies for prostate cancer, skeletal-related events, and PFS2 up to final OS analysis.

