8.1.4. Time Period for Collecting AE/SAE Information

The time period for actively eliciting and collecting AEs and SAEs (“active collection period”) for each subject begins from the time the subject provides informed consent, which is obtained before the subject’s participation in the study (ie, before undergoing any study-related procedure and/or receiving investigational product), through and including a minimum of 30 days after the last administration of the investigational product.

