8.1.5. Reporting SAEs to Pfizer Safety

All SAEs occurring in a subject during the active collection period are reported to Pfizer Safety on the CT SAE Report Form.

SAEs occurring in a subject after the active collection period has ended are reported to Pfizer Safety if the investigator becomes aware of them; at a minimum, all SAEs that the investigator believes have at least a reasonable possibility of being related to investigational product must be reported to Pfizer Safety.

Follow up by the investigator continues throughout and after the active collection period and until the event or its sequelae resolve or stabilize at a level acceptable to the investigator, and Pfizer concurs with that assessment.

If a patient begins a new anticancer therapy, SAEs occurring during the above-indicated active collection period must still be reported to Pfizer Safety irrespective of any intervening treatment.

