18.2. Open-Label Study Period

Day 1 of the OL period will occur after consent is signed and eligibility is verified. Patients will continue their assigned treatment, return for safety follow-up within approximately 30 days after last dose, and will enter long-term follow-up.

Sites must have all OL Day 1 visits completed within 16 weeks after IRB/EC approval of this protocol amendment (see [Figure 3](#)).

Figure 3. Schematic – Open-Label Treatment Period

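### Open-label Table 16 note 10 ends adverse-event collection at a safety visit that may precede day 30, in conflict with Sections 8.1.4 and 18.3.2 for all events and, after new therapy, with 8.1.5, 8.1.6 and 8.5.5 for serious events

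*Protocol*

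**What the plan says.** **End of collection, open-label schedule.** Note 10 of Table 16 (Protocol Section 18.1) directs sites to "Collect serious and nonserious adverse event information from the time of signing of informed consent through safety follow-up". It then adds: "If no safety follow-up, collect adverse event information through 30 days after the last dose of study drug". The window row reads "Windows [4] na ±5 ±7 na ±7 ±7"; the fifth entry, ±7 days, belongs to the safety follow-up column. Note 3 places that visit about 30 days after last dose, but if new antineoplastic treatment begins sooner, "then safety follow-up will occur immediately before starting the new treatment". Section 18.8 repeats this rule. Section 18.2 has patients "return for safety follow-up within approximately 30 days after last dose".

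**End of collection, elsewhere.**
- Section 8.1.4 sets the active collection period "through and including a minimum of 30 days after the last administration of the investigational product".
- Section 8.1.5, on patients who begin a new anticancer therapy: "SAEs occurring during the above-indicated active collection period must still be reported to Pfizer Safety irrespective of any intervening treatment".
- Section 8.1.6 stops non-serious recording when new anticancer therapy starts, but keeps serious adverse events (SAEs) on the case report form for the whole active period.
- Section 8.5.5 collects SAEs to 30 days after last dose.
- Section 18.3.2, within the supplement itself, continues safety data collection through 30 days after last dose and refers to Section 8.
- Appendix 5 note 17, the double-blind counterpart of note 10, has the 30-day minimum.
- SAP Section 3.5 ends the on-treatment period at a minimum of 30 days after last dose, or on the day before new antineoplastic drug therapy.

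**Open-label Day 1.** Note 1 states: "OL Day 1 will be the next regularly scheduled visit following approval and activation of this protocol amendment at the study site". In Table 16, adverse-event monitoring is marked at week 13 and every 12 weeks, at unscheduled visits and at safety follow-up. Drug accountability is marked at week 13 and every 12 weeks and at safety follow-up. Both rows are blank at Day 1. The regular visit that Day 1 replaces (Table 6 and Appendix 5) included both.

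**The concern.** Note 10 ties the end of collection to a visit rather than to a number of days after last dose, and the visit can move earlier. A site working from the schedule would close collection at that visit and have no scheduled adverse-event contact afterwards, because the monitoring row is blank in the long-term follow-up column. What could be lost is active elicitation of events, serious ones included, in the last part of the 30-day period. Men who move quickly to another therapy are the most exposed.

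At the other end, the first open-label visit closes the last interval under the previous schedule. With no adverse-event step marked there, events from that interval are next formally elicited at open-label week 13. The accountability blank matters because this is the point at which placebo capsules stop, and Section 18.4.1 ties bottle returns to the accountability visits in Table 16.

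**Working it through.** The plan gives no figure to reproduce. The check is day arithmetic and a comparison of rules.

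**1. When the safety visit can occur.** Inputs: about day 30 (note 3) and ±7 days (Table 16). Earliest in-window day = 30 − 7 = 23; latest = 30 + 7 = 37. The double-blind window was −3 to +10 days (Section 5.4), so 30 − 3 = day 27 to 30 + 10 = day 40. There the 30-day minimum in Appendix 5 note 17 applied whatever the visit date.

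**2. Early visit, no new therapy.** For a visit on day v, note 10 leaves 30 − v days uncovered.
- v = 23: 30 − 23 = 7 days; 7/30 = 23% of the period.
- v = 29: 30 − 29 = 1 day; 1/30 = 3%.

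These days fall inside the active period of Sections 8.1.4 and 18.3.2 for serious and non-serious events alike.

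**3. Visit brought forward by new therapy starting on day d.** Taking the visit as falling at day d, 30 − d days are uncovered.
- d = 29: 1 day; d = 5: 25 days; d = 1: 29 days.

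| Event type after day d | Note 10 | Sections 8.1.5, 8.1.6, 8.5.5 | Conflict |
|---|---|---|---|
| Serious | Stops at the visit | Continues to day 30 | Yes, 30 − d days |
| Non-serious | Stops at the visit | Recording ends at new therapy (8.1.6) | None |

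**4. Consistency within note 10.** A man who has no safety visit is covered to day 30. A man seen on day 23 is covered to day 23. The better-followed patient has the shorter collection period.

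**5. Which analyses are touched.** Events missed under step 2 fall inside the SAP on-treatment period and would belong in the treatment-emergent tables. SAEs missed under step 3 occur on or after the start of new therapy, outside that period, so SAP Section 3.5 would list them without summarizing them. The loss there is to SAE reporting and listings. Deaths are tabulated from the survival follow-up forms (SAP Section 6.8.2), and survival follow-up continues regardless.

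**6. Open-label Day 1.** Visits are 12 weeks apart, so 12 × 7 = 84 days. Last double-blind visit to open-label Day 1: 84 days. Day 1 to week 13 (study day 85): 84 days. With no review marked at Day 1, the nominal gap between scheduled reviews is 84 + 84 = 168 days; with one marked it is 84.

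**The case against.** The best defence is that the obligation is stated correctly elsewhere. Section 18.3.2 is the body text of the supplement, runs to 30 days and points to Section 8, and note 10 also mentions Section 8. Section 8.1.5 further requires SAEs after the active period to be reported if the investigator becomes aware of them. Harm therefore needs a site to follow the footnote alone. That is fair and limits the severity. But no passage says that Section 8 overrides the schedule, and note 10 is not merely silent: it names a different end point and confines 30 days to the no-visit case.

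Several stronger readings are tempting and are not supported.
- *A visit at day 5 loses 25 of 30 days of all safety data.* Section 8.1.6 and the SAP on-treatment period both support ending non-serious recording at new therapy. The 25 days concern SAEs only.
- *The half-life sizes the loss.* The 5.8-day figure in the protocol describes how much enzalutamide remains. It does not estimate missed events, and it does not apply to men on placebo plus leuprolide.
- *The blank at Day 1 contradicts the collection rules.* Sections 8.1.4 and 18.3.2 keep collection running, Section 8.1.2 requires questioning about events without tying it to marked visits, and no passage requires a mark at every visit. Day 1 also includes a symptom-directed examination, local laboratory tests and a medication review.
- *Skeletal events are missed at Day 1.* The follow-up assessments row is marked at Day 1, and note 19 includes skeletal-related events.
- *Late elicitation moves events between the double-blind and open-label stages.* SAP Section 3.5 classifies treatment-emergent events by onset date, so asking later does not by itself reassign them. What remains is poorer recall.

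**Conclusion.** Note 10 is inconsistent with the protocol's own collection period and should be corrected. The conflict covers all adverse events for 1 to 7 days when the safety visit falls on days 23 to 29 without new therapy, and SAEs only for 1 to 29 days when new therapy brings the visit forward. There is no conflict for non-serious events after new therapy. The Day 1 blanks for adverse-event review and drug accountability are a scheduling omission that doubles the nominal gap between scheduled reviews, once per continuing patient.

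This rests on three assumptions: the ±7-day window is centred on day 30; visits occur on their target days; and the blank cells reflect the intended layout of Table 16, which should be confirmed against the laid-out page. The number of patients or events affected cannot be estimated, because the documents do not say how many men enter the open-label period, how often the safety visit is early, or how often new therapy starts within 30 days.

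**What to change.** **Note 10.** Reword it to match Sections 8.1.4 to 8.1.6, 8.5.5 and 18.3.2. For example: *Collect serious and non-serious adverse events through a minimum of 30 days after the last dose of study drug, even if the safety follow-up visit is earlier. If new anticancer therapy starts within that time, stop recording non-serious events at its start and continue to collect and report serious events to day 30.* A rule that extended all events to the later of the visit and day 30 would go too far, because it would contradict Section 8.1.6.

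**Day-30 contact.** A short telephone check at day 30 when the visit is earlier is optional. It gives sites a practical way to meet the minimum.

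**Table 16.** Mark open-label Day 1 for adverse-event monitoring and study drug accountability, covering the interval since the last double-blind visit. No added skeletal-event mark is needed. Where Day 1 has already taken place, a site reminder to confirm at the next visit that the preceding interval was reviewed would serve the same purpose.

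**Cost.** One footnote, two table marks and, if adopted, one call per early visit. No endpoint, analysis or treatment rule changes.

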18.1.1. Blinding

[figure not shown]
Participants will be unblinded to their assigned study intervention at the start of this OL study period. Investigators and other site staff will be unblinded to participants’ assigned study intervention. Sponsor staff will be unblinded to participants’ assigned study intervention.

18.2. Open-Label Study Period

Day 1 of the OL period will occur after consent is signed and eligibility is verified. Patients will continue their assigned treatment, return for safety follow-up within approximately 30 days after last dose, and will enter long-term follow-up.

Sites must have all OL Day 1 visits completed within 16 weeks after IRB/EC approval of this protocol amendment (see [Figure 3](#)).

Figure 3. Schematic – Open-Label Treatment Period

